### STUDY WITH TITLE:

# "Prebiotic and Anti-inflammatory Effects of a Pectin Polysaccharide"

#### STUDY PROTOCOL

#### Task 1: Evaluation of prebiotic effects RG-I

The dietary fibre fractions from RG-I will be tested for their prebiotic potential. Thus, the effects of these fibres on short chain fatty acid (SCFA) profile, microbiota composition and microbiota-associated metabolites will be investigated. In this Task, batch culture fermentation systems containing basal growth medium will be inoculated with faecal homogenates obtained from healthy subjects and RG-I. Samples from the in vitro fermentation will be obtained from different time points and will be used for analyzing microbiota composition and microbiota-associated metabolites. Subjects will complete validated questionnaires related to their dietary intake and a Gastrointestinal Symptom rating scale (GSRS-IBS) in this Task.

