#### STATISTICAL ANALYSIS

All statistical tests will be assessed using One Way ANOVA with a nominal significance level of 5% and post hoc testing of treatment contrasts with Tukey's HSD. The primary endpoint analysis will be based on fibre effect on the intestinal barrier function in terms of FITC passage, and whether there is a difference between treatments across all healthy subjects. Secondary endpoints include HRP quantification (supernatant), TEER values (electrophysiological parameter).

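### Task 1 fermentations involve several faecal donors and several time points, but the plan sets One Way ANOVA for every test, with no donor term and no named time point or summary

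*Combined protocol and SAP*

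**What the plan says.** Under Task 1, the batch cultures are "inoculated with faecal homogenates obtained from healthy subjects and RG-I". The donors are plural, but their number is not given. The section does not say whether stool is mixed or kept separate by donor, or whether each donor's stool meets every treatment. On sampling it says "Samples from the in vitro fermentation will be obtained from different time points", without giving how many or when, or whether the same vessel is sampled repeatedly. The aim is broad: "the effects of these fibres on short chain fatty acid (SCFA) profile, microbiota composition and microbiota-associated metabolites will be investigated".

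The Statistical Analysis section covers all of this with one rule: "All statistical tests will be assessed using One Way ANOVA with a nominal significance level of 5" per cent, followed by "post hoc testing of treatment contrasts" by Tukey's method. It names no block, time factor, repeated-measures or mixed model, time point or summary over time. Its only mention of subjects, "whether there is a difference between treatments across all healthy subjects", belongs to the primary endpoint (FITC passage, Task 2). The named secondary endpoints, HRP and TEER, also belong to Task 2.

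**The concern.** One Way ANOVA has a single factor. Task 1 describes three sources of structure: treatment, donor and time. The rule for all tests leaves two questions open.

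- **Donor.** If every donor's inoculum is run under every treatment, treatment differences can be taken within donor. One Way ANOVA does not use this. Donor variance cancels from the treatment differences but stays in the error term, so real fibre effects are more easily missed.
- **Time.** With several time points and no rule, an analyst could test one, average them, test each, or pool all samples. These choices have different error rates. Tukey's method adjusts treatment contrasts within one ANOVA, not across time points.

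At stake is the reliability of the Task 1 comparisons, which carry the prebiotic aim.

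**Working it through.** **Inputs.** From the documents: the 5% level, One Way ANOVA for all tests, more than one donor and more than one time point. The documents give no sample size, number of treatments, variance or effect size, so there is no planned figure to reproduce and everything below is assumed for illustration. Base case: 10 donors, 3 treatments, 4 time points, total variance 1 (donor 0.3, vessel 0.3, residual 0.4), and a 0.9 SD shift in one arm. Simulated results use 20,000 runs per setting.

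**1. One time point, donors crossed with treatments**

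- Variance relevant to treatment differences: 1 − 0.3 = 0.7.
- Expected error mean square: 1 for One Way (27 df), 0.7 with donor as a block (18 df).
- Type I error, One Way: the critical F(2, 27) is 3.354. Under no effect the One Way statistic behaves approximately like 0.7 × F, so rejection needs F > 3.354/0.7 = 4.79. With 2 numerator df, P(F > x) = (1 + 2x/ν)^(−ν/2). This gives (1 + 9.58/27)^(−13.5) ≈ 0.017. Simulation gives 1.8% to 1.9%. Blocked: 5%.
- Power: the sum of squared arm deviations is 0.6² + 0.3² + 0.3² = 0.54. Noncentrality = 10 × 0.54/0.7 = 7.71. The noncentral F gives 62% blocked and about 46% for One Way. Simulation agrees.

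**2. Sensitivity of power (vessel share 0.3)**

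| Setting | One Way | Blocked |
|---|---|---|
| 10 donors, donor share 0 | 49% | 47% |
| 10 donors, donor share 0.1 | 48% | 51% |
| 10 donors, donor share 0.3 | 46% | 62% |
| 10 donors, donor share 0.5 | 44% | 78% |
| 6 donors, donor share 0.3 | 24% | 36% |
| 20 donors, donor share 0.3 | 85% | 93% |
| 10 donors, donor share 0.3, mean over time, constant effect, vessels resampled | 65% | 86% |

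The choice of summary matters too. If the effect appears only at the last two time points, the blocked time mean has 31% power, against 62% at the last time point.

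If each treatment has different donors, One Way ANOVA at one time point or on the mean has a type I error of about 5%.

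**3. If all time points were pooled as independent samples**

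Each arm then has 10 × 4 = 40 samples, with 117 error df and a critical F of 3.07. Let V be the variance per sample relevant to treatment differences, and W be 40 × the variance of an arm mean. The expected error mean square is (40 − W)/39. The F statistic is then scaled by roughly V ÷ [(40 − W)/39]. With no time trend:

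| Design | V | W | Scale | Type I error (approximate) | Simulated |
|---|---|---|---|---|---|
| Crossed, vessels resampled | 0.4 + 4×0.3 = 1.6 | 0.4 + 4×0.6 = 2.8 | 1.68 | 16% | 17% |
| Crossed, fresh vessel each time | 0.7 | 0.7 + 4×0.3 = 1.9 | 0.72 | 1.6% | about 2% |
| Different donors, fresh vessel | 1.9 | 1.9 | 1.94 | 21% | 21% |
| Different donors, vessels resampled | 2.8 | 2.8 | 2.94 | 35% | 36% |

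A time trend adds to the error term and pulls these down. With a rise of 1 SD per time point, the first row falls to about 1.5% and the third to about 2.8%. The direction is therefore not fixed.

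**4. If each of four time points were tested at 5% without adjustment**

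For independent tests the chance of at least one false positive is 1 − 0.95⁴ = 18.5%. In the crossed base case it is about 6%, because each test runs near 2%. If donors do not differ it is roughly 13% to 19%, depending on how strongly time points correlate within a vessel.

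**The case against.** The strongest reply is that the plan commits to none of the harmful analyses. It does not say that time points will be pooled or tested one by one, and One Way ANOVA at a single time point is compatible with the text. Nor does it say that donors are crossed with treatments. With mixed inocula there is no donor term to add. With different donors per treatment no block is possible, and One Way ANOVA on one summary is valid. The Task 1 outcomes are not named endpoints and can be read as exploratory. If donors differ little, blocking gains little (48% against 51% at donor share 0.1).

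Much of this stands. It limits the donor part to a conditional statement and makes the time part an unfilled gap rather than a stated error. It does not remove the point, because the rule covers all tests at a nominal 5% without calling any exploratory, and the time gap remains under every inoculum design.

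Three stronger readings are tempting but unsupported.

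- **That the plan inflates false positives.** At one time point or on one summary, One Way ANOVA is conservative or correct. Inflation needs pooling or repeated unadjusted testing, neither of which is planned.
- **That pooling would be safe if a fresh vessel were used each time.** That holds only for crossed donors. With different donors per treatment, the same donors recur at each time point and pooling gives 21% in the base case.
- **That the primary result is affected.** "The primary endpoint analysis will be based on fibre effect on the intestinal barrier function in terms of FITC passage", a Task 2 measurement outside this point.

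**Conclusion.** The point holds in conditional form and should be corrected, with medium confidence. The plan's single test does not match the data structure that Task 1 describes, and it leaves the unit of analysis and the tested time point undefined. If donors are crossed with treatments and differ from each other, the likely harm is missed fibre effects: in the base case, 16 points of power at one time point (62% − 46%) and 21 points on the time mean (86% − 65%). The size depends on the assumed donor share and number of donors, and the loss disappears if donors do not differ. The false-positive figures only show why a time rule is needed; they do not describe what the plan proposes. The consequence is confined to SCFA, microbiota and metabolite comparisons.

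**What to change.** - State whether each donor's inoculum is kept separate and run under every treatment, mixed, or used for one treatment only. State also whether vessels are sampled repeatedly.
- For each Task 1 outcome, pre-specify one time point or one summary over time (such as the mean or AUC) that suits when the effect is expected. For microbiota composition, first name the univariate summaries to be tested. Do not pool time points as independent samples.
- If donors are crossed with treatments, compare treatments with donor as a block, or with a mixed model with donor random (and vessel within donor random if vessels are resampled). Keep the Tukey-adjusted contrasts.
- If inocula are mixed or donors differ by treatment, keep One Way ANOVA on the chosen time point or summary.

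Cost: SAP wording and slightly more analysis work, with no extra samples. If donors turn out not to differ, blocking gives up about 2 to 3 points of power with 10 donors. Time points not chosen become supportive only.

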#### Task 2: Evaluation of the effects of RG-I fractions on intestinal permeability

By using a sigmoidoscopy procedure, colon biopsies will be collected from the subjects, where the collected biopsies will be mounted in Ussing Chambers in order to investigate the effects of the fibre fractions on intestinal permeability. Supernatants collected from Task 1 will be added to the mucosal side of the biopsy together with a stressor and two permeability markers. Samples will subsequently be collected from the serosal side and will be used to measure the permeability markers related to paracellular and transcellular permeability.

#### STATISTICAL ANALYSIS

All statistical tests will be assessed using One Way ANOVA with a nominal significance level of 5% and post hoc testing of treatment contrasts with Tukey's HSD. The primary endpoint analysis will be based on fibre effect on the intestinal barrier function in terms of FITC passage, and whether there is a difference between treatments across all healthy subjects. Secondary endpoints include HRP quantification (supernatant), TEER values (electrophysiological parameter).

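### The FITC, HRP and TEER tests use a One Way ANOVA with no subject term or stated unit of analysis; if treatments share subjects, as the text suggests but does not state, the error term is wrong

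*Combined protocol and SAP*

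**What the plan says.** The STATISTICAL ANALYSIS section is one paragraph. It states: "All statistical tests will be assessed using One Way ANOVA with a nominal significance level of 5" per cent, followed by "post hoc testing of treatment contrasts" using Tukey's HSD. The rule covers the primary endpoint, FITC passage, and the secondary endpoints HRP and TEER. The primary question is "whether there is a difference between treatments across all healthy subjects".

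Task 2 describes the material: "colon biopsies will be collected from the subjects, where the collected biopsies will be mounted in Ussing Chambers". Treatment is applied in the chamber: "Supernatants collected from Task 1 will be added to the mucosal side of the biopsy".

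The documents do not give the number of subjects, the number of treatments, the biopsies per subject, the chambers per subject and treatment, or how chambers are assigned to treatments. They do not say whether one observation is a chamber, a biopsy or a subject mean. No subject, block, repeated-measures or random term is named.

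**The concern.** A One Way ANOVA assumes that all observations are independent apart from treatment. Three features of the plan point away from that. Treatment goes onto the biopsy, not into the person. Several biopsies come from the subjects. No subject is allocated to a treatment. The natural inference is that biopsies from one subject are exposed to several treatments, which makes subject a block.

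On that reading, the one-way error mean square contains between-subject variance that does not affect the treatment comparison, and Tukey's HSD uses the same mean square. The consequence depends on how replicate chambers are handled and on how much treatment response varies from subject to subject. The primary conclusion rests on this test, so a real fibre effect on FITC passage could be missed or, under narrower conditions, a false one declared.

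**Working it through.** The only numerical input in the documents is the 5% level; there is no sample size or power figure to reproduce. All sizes and variances below are assumptions for illustration.

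**Model.** For n subjects, k treatments and r chambers per subject and treatment, FITC = treatment + subject (variance Vs) + subject-by-treatment (Vst) + chamber residual (Ve), with total variance 1.

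**Case 1: one value per subject and treatment (r = 1).** If there is no treatment effect:
- E[MS treatment] = Ve + Vst
- E[MS error, one-way] = Ve + Vst + Vs
- E[MS error, subject-blocked] = Ve + Vst

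The one-way denominator is too large by Vs, so the test is conservative whenever Vs > 0. The same holds if replicate chambers are first averaged.

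Take n = 12, k = 4, Vst = 0, and one treatment shifted by 0.8 total SD. ICC is the subject share of variance. Error degrees of freedom are 4 × 11 = 44 (one-way) and 3 × 11 = 33 (blocked). The ratio of Tukey interval widths, one-way to blocked, is [q(4,44)/q(4,33)] × √(1/(1−ICC)), with q(4,44)/q(4,33) = 0.987. Power and type I error are simulated.

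| ICC | One-way power | Blocked power | One-way type I error | Tukey width ratio |
|---|---|---|---|---|
| 0 | 46% | 45% | 5.0% | 0.99 |
| 0.1 | 44% | 49% | 3.5% | 1.04 |
| 0.3 | 41% | 61% | 1.4% | 1.18 |
| 0.5 | 36–37% | 77% | 0.4% | 1.40 |

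Across n of 8, 12 and 20 with 3 to 5 treatments and the same shift, the power shortfall is roughly 12–23 points at ICC 0.3 and 20–45 points at ICC 0.5. At ICC 0 the one-way test gains about 1–2 points.

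**Case 2: replicate chambers entered as independent (r > 1).** If there is no treatment effect:
- E[MS treatment] = Ve + r·Vst
- E[MS error, one-way] = Ve + [r(n−1)/(nr−1)]·(Vs + Vst)

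The numerator exceeds the denominator when n(r−1)·Vst > (n−1)·Vs, that is, when Vst/Vs exceeds (n−1)/(n(r−1)). For n = 12 this is 11/12 = 0.92 with two chambers and 11/24 = 0.46 with three. This marks approximately where inflation begins, because the pooled statistic does not follow an exact F distribution.

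Simulated type I error, n = 12 and k = 4:

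| Chambers | Vs | Vst = 0 | 0.1 | 0.2 | 0.3 |
|---|---|---|---|---|---|
| 2 | 0.4 | 0.8% | 1.6% | 3.0% | 4.6% |
| 3 | 0.4 | 0.7% | 3.1% | 6.3% | 11.0% |
| 2 | 0.2 | 2.4% | 3.8% | 5.6% | 7.5% |
| 3 | 0.2 | 2.4% | 5.6% | 9.7% | 14.7% |

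Pooling chambers is therefore conservative in some cells and anti-conservative in others. A subject-blocked ANOVA on subject-by-treatment means holds about 5% in every cell.

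**Case 3: subjects not shared.** If each subject receives one treatment and contributes one value or mean, One Way ANOVA is correct. If that subject's chambers are instead entered separately (12 subjects per treatment, 4 treatments), type I error with two and three chambers is 9% and 14% at ICC 0.2, and 14% and 23% at ICC 0.4.

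**The case against.** The strongest objection is that shared subjects are an inference. Task 2 never says that each subject's biopsies receive every treatment, and the phrase "whether there is a difference between treatments across all healthy subjects" also fits a plain pooled comparison. The statistical section is very short, so One Way ANOVA may be shorthand for a single treatment factor, with blocking or averaging left undescribed. This stands as a limit on certainty. What the text firmly shows is that the design and unit of analysis are unspecified; the wrong error term follows only on the inferred reading and only if subjects differ. It does not remove the point, because the test as written is right only if each subject gives one value to one treatment, or if within-subject correlation is zero. The text establishes neither.

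A reader might infer that the handling of replicates alone decides the direction of the error, so that pooling chambers must inflate false positives. That is not so. With two pooled chambers and a subject share of 0.4, all four cells above stay below 5%. Inflation also needs enough subject-by-treatment variance, and nothing in the documents says that chambers will be pooled.

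It is also fair to object that every size shown rests on assumed values. The figures show the pattern and cannot be read as estimates for this trial.

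**Conclusion.** The point holds, with medium confidence, and should be fixed before the data are analysed. On the reading that treatments share subjects, and if subjects differ, the One Way ANOVA and its Tukey contrasts use the wrong error term for FITC passage, HRP and TEER. The likely harm is lost power and intervals that are too wide. In the 12-subject, 4-treatment illustration the loss is about 20 points at ICC 0.3 and about 40 at 0.5, but only about 5 at 0.1.

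A reader might conclude that false-positive control is lost altogether. The documents do not support that: with one value or mean per subject and treatment, type I error stays at or below 5%. Anti-conservatism under shared subjects requires both replicate chambers treated as independent and a variance ratio Vst/Vs above about (n−1)/(n(r−1)). Neither condition can be settled from the text, and the size for this trial cannot be fixed.

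**What to change.** State the biopsies per subject, the treatments per subject, how chambers are assigned to treatments, and the unit of analysis. Then replace the One Way ANOVA sentence with wording such as:

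> FITC passage, HRP and TEER will be averaged over replicate chambers within subject and treatment and analysed with treatment as fixed effect and subject as block (or random effect); Tukey contrasts will use that model's error term.

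A chamber-level mixed model with subject and subject-by-treatment random terms is an alternative. It is equivalent only with balanced data, non-negative variance estimates and suitable denominator degrees of freedom. Adding a subject term to pooled chambers without averaging or an interaction term is not enough: in the 12-subject, 4-treatment setting it gives type I error of about 8–32% at subject-by-treatment shares of 0.1–0.3.

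If each subject in fact receives only one treatment, keep One Way ANOVA on one mean per subject.

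The cost is SAP wording only, with no new subjects, biopsies or measurements. Error degrees of freedom fall, for example from 44 to 33 with 12 subjects and 4 treatments, which costs about 1–2 points of power if the within-subject correlation is zero.

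### One-way ANOVA for every test does not suit microbiota composition: it cannot test the whole profile, ignores donor, and can show false decreases if data are relative abundances

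*Combined protocol and SAP*

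**What the plan says.** The Statistical Analysis section gives one method for everything: "All statistical tests will be assessed using One Way ANOVA with a nominal significance level of 5" (per cent), followed by "post hoc testing of treatment contrasts with Tukey's HSD". It makes no exception and has no separate paragraph for Task 1.

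Task 1 states that "the effects of these fibres on short chain fatty acid (SCFA) profile, microbiota composition and microbiota-associated metabolites will be investigated". It adds that "Samples from the in vitro fermentation will be obtained from different time points and will be used for analyzing microbiota composition and microbiota-associated metabolites". Composition is therefore something the study intends to analyse, and the only stated test for it is one-way ANOVA.

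Composition is not a named endpoint. "The primary endpoint analysis will be based on fibre effect on the intestinal barrier function in terms of FITC passage", and "Secondary endpoints include HRP quantification (supernatant), TEER values (electrophysiological parameter"). The verb leaves the secondary list open, but microbiota is not on it.

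The document does not say whether composition is recorded as relative abundance, counts or absolute amounts, whether data are transformed, or whether taxa are tested one at a time. It gives no number of donors, treatments, time points or taxa.

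**The concern.** Three features of the stated method do not fit this outcome.

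1. **The whole profile is not tested.** One-way ANOVA handles one response at a time. It gives no single answer to whether composition differs between treatments. Tukey's HSD adjusts across treatment contrasts for one response, not across taxa. This holds on any measurement scale.
2. **Donor is ignored.** Cultures are inoculated with faecal material from healthy subjects, and the statistical section speaks of treatment differences across all subjects. This reads as each donor's material being exposed to each treatment. A one-way model leaves donor variation in the error term.
3. **Relative data carry an artefact.** If shares are analysed, they sum to one, so growth of one taxon forces the others down. Task 1 looks for prebiotic potential, so selective growth is the result hoped for, and the artefact appears when the hypothesis is true.

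At stake is the Task 1 statement about which bacteria RG-I raises or lowers.

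**Working it through.** The plan has no sample size, power or variance to reproduce. The 5% level is its only numerical design figure.

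**Step 1: closure arithmetic.** Let one taxon have starting share p and grow f-fold while the others keep their absolute amounts. The total becomes 1 + p(f − 1), so every other share is multiplied by 1/(1 + p(f − 1)). The starting shares and growth factors are assumptions.

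| p | 2-fold | 4-fold | 8-fold |
|---|---|---|---|
| 5% | 1/1.05: −4.8% | 1/1.15: −13.0% | 1/1.35: −25.9% |
| 10% | 1/1.10: −9.1% | 1/1.30: −23.1% | 1/1.70: −41.2% |
| 20% | 1/1.20: −16.7% | 1/1.60: −37.5% | 1/2.40: −58.3% |

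**Step 2: how often an unaffected taxon is called significant.** This is a simulation in which every input is assumed: 20 taxa, one responder at 10%, two treatments on each donor's material, one time point, log-scale donor SD 0.6, within-donor SD 0.4, and 10 or 20 donors. With two treatments, one-way ANOVA equals the unpaired t test. CLR is the centred log-ratio. Rates are per unaffected taxon, for 10/20 donors, nominal 5%.

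| Growth | One-way ANOVA on shares | Donor-blocked CLR |
|---|---|---|
| 2-fold | about 0.6% at either size | 5.2%/5.9% |
| 4-fold | 2.4%/5.7% | 6.2%/8.4% |
| 8-fold | 16%/40% | 8%/13% |

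The planned test is far below 5% at 2-fold growth because donor variation inflates its error term. With no growth it rejects only 0.1% to 0.3%. Its low error at modest growth therefore comes from one fault offsetting another. If donor blocking is added but raw shares are kept, the rates are 16%/32% at 4-fold and about 45%/79% at 8-fold growth.

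**Step 3: at least one false finding, and power.** At 4-fold growth, at least one of the 19 unaffected taxa is falsely significant in about 37%/66% of studies with the planned test, against 13%/20% with donor-blocked CLR and Benjamini-Hochberg (BH). That comparison changes two things at once. Nineteen independent tests at an exact 5% already give 1 − 0.95^19 = 62%, so blocked CLR without BH is worse than the planned test on this measure. A rerun of the same model separates the two effects (10/20 donors):

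| | Planned, no BH | Planned, BH | Blocked CLR, no BH | Blocked CLR, BH |
|---|---|---|---|---|
| Any false taxon, 4-fold | 38%/65% | 2%/4% | 73%/84% | 14%/21% |
| Any false taxon, 8-fold | 92%/100% | 22%/67% | 85%/96% | 20%/33% |
| Responder found, 2-fold | 45%/89% | 4%/29% | 91%/100% | 44%/96% |

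The power loss from leaving out donor is clear on equal terms. At 2-fold growth with 10 donors, the responder is found in 44% of studies against 92% without multiplicity control (45% and 91% in the rerun), and in 4% against 44% with it.

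**Step 4: sensitivity.** A second model used three independent arms, log shares, log-SD 0.3 to 1.0 and 6 to 20 per arm. The per-taxon rate on shares ran from 5.2% to 16.0% at 2-fold, 6.1% to 78.7% at 4-fold and 9.8% to 100% at 8-fold growth. On absolute amounts it stayed near 5% throughout. CLR reached 18.6% in its worst setting (20 per arm, log-SD 0.3, 8-fold).

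**The case against.** The strongest reply is that the document never says composition is expressed as shares. A reader might infer that it must be, and that following the plan will report suppressed taxa. The text does not support that. With absolute quantification the artefact is absent, and even with shares a significant false decrease depends on growth, starting share, variability and sample size. At 2-fold and 4-fold growth in the donor model, the planned test's per-taxon error is at or below about 6%. Only the 8-fold case, which nothing in the document makes likely or unlikely, shows serious per-taxon inflation. This stands, and the point is worded conditionally for that reason.

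Second, the closure artefact comes from the relative scale, not from ANOVA. Any taxon-by-taxon test on raw shares has it, and ANOVA on log-ratios or absolute amounts would still comply with the plan's sentence. This also stands. The ANOVA rule itself is at fault for offering no test of the whole profile and for omitting donor.

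Third, the 45%/79% figures belong to a donor-blocked analysis of shares, which the plan does not propose. That is correct. They are a warning against repairing the blocking alone.

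Fourth, composition is neither the primary nor a named secondary endpoint. True, and this limits the weight of the point. It is still an outcome the study says it will analyse, under the only method it states.

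**Conclusion.** The concern holds in conditional form. Whatever the scale, the stated method has no test of overall composition. It also discards donor information if, as the text suggests, treatments are compared within donor; if faecal material is pooled, that part falls away. If relative abundances are used, unaffected shares fall by 9%, 23% and 41% at 2-, 4- and 8-fold growth from a 10% start, and this can be read as a fibre effect.

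Under the donor model, per-taxon false significance with the planned test ranges from about 0.6% (2-fold) to 16%/40% (8-fold). The lower chance of any false taxon at 4-fold growth (13%/20% against 37%/66%) comes from BH control, not from the log-ratio. What blocking and log-ratios add is power at modest growth, and less bias at large growth with 20 donors.

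It would go too far to say that the Task 1 conclusions will be wrong or that the trial's main result is in doubt. FITC passage, HRP and TEER are not touched by this point. It is a recommended correction to a part of the plan outside the named endpoints.

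**What to change.** Amend the Statistical Analysis section so that microbiota composition is exempt from the one-way ANOVA rule, and state:

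- the measurement scale (relative or absolute) and whether each donor's material receives every treatment;
- one overall multivariate test with permutation within donor, for example permutational multivariate ANOVA on Aitchison distance;
- taxon-level tests with donor as block and BH control at 5%, on log-ratio values if the data are relative, or on absolute amounts if absolute quantification is available;
- that changes in raw shares are described as relative only.

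The log-ratio route costs SAP wording and standard software, with no new samples; absolute amounts apply only if such measurements are made. On the log-ratio route a zero-replacement rule must be fixed in advance and results are on a ratio scale. CLR reduces the bias without removing it: about 8%/13% per taxon at 8-fold growth with 10/20 donors before BH. BH also costs power (91% to 44% for the responder at 2-fold growth with 10 donors in the rerun), which is the price of testing many taxa. Absolute amounts avoid the closure bias and are preferable for the taxon-level tests where they exist.

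### A one-way ANOVA on treatment alone leaves subject and biopsy differences in the error term; a subject block and a pre-exposure TEER covariate would recover precision cheaply

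*Combined protocol and SAP*

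**What the plan says.** The Statistical Analysis section sets one method for every endpoint: "All statistical tests will be assessed using One Way ANOVA", then "post hoc testing of treatment contrasts with Tukey's HSD". The primary analysis concerns the "fibre effect on the intestinal barrier function in terms of FITC passage" and asks "whether there is a difference between treatments across all healthy subjects". HRP and "TEER values (electrophysiological parameter" are secondary. No covariate, starting value, subject term or biopsy term is named. The time point and scale of TEER (raw, change, or percent of a starting value) are not given.

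The Task 2 section has colon biopsies mounted in Ussing chambers, after which "Supernatants collected from Task 1 will be added to the mucosal side of the biopsy together with a stressor and two permeability markers". It describes no resistance reading before that addition. That each biopsy receives a single condition is implied by the set-up but not stated.

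**The concern.** A one-way ANOVA splits the variation into treatment and everything else. If subjects supply biopsies to several treatments, two avoidable sources end up in everything else: differences between subjects, and differences in starting integrity between biopsies from the same subject. Tukey's HSD uses the same residual mean square, so each pairwise comparison is widened as well.

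Both sources can be reduced. A subject block removes the first but cannot touch the second. A TEER reading taken before exposure may remove part of the second. TEER is already an endpoint, so resistance is to be measured anyway, and the order of steps in Task 2 leaves a window between mounting and exposure. Because the reading precedes exposure, the treatment cannot affect it. At stake is the power of the primary FITC comparison and of the HRP and TEER comparisons.

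**Working it through.** The plan states no sample size, SD, effect size, number of treatments or number of biopsies, so there is no figure of its own to reproduce. From the documents come only the model (treatment as the single term), the 5% level and the endpoints. Everything else below is an assumption.

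**1. What the covariate can remove.** Let ρ be the within-subject correlation between pre-exposure TEER and the outcome. Adjustment multiplies the residual variance by 1 − ρ². The equivalent gain in sample size is 1/(1 − ρ²).

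| Assumed ρ | 1 − ρ² | Fall in residual variance | Equivalent sample-size factor |
|---|---|---|---|
| 0 | 1.00 | 0% | 1.00 |
| 0.2 | 0.96 | 4% | 1.04 |
| 0.3 | 0.91 | 9% | 1.10 |
| 0.5 | 0.75 | 25% | 1.33 |
| 0.7 | 0.51 | 49% | 1.96 |

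**2. What the covariate costs.** With *d* error degrees of freedom before adjustment, the adjusted variance is about (1 − ρ²)(1 + 1/(d − 2)) of the unadjusted one. Break-even is therefore at ρ = √(1/(d − 1)):

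- 24 biopsies, 4 groups, no block: d = 20, ρ = √(1/19) = 0.23.
- 40 biopsies, 4 groups, no block: d = 36, ρ = √(1/35) = 0.17.
- 10 subjects × 4 treatments, blocked: d = 9 × 3 = 27, ρ = √(1/26) = 0.20.

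**3. Illustrative power by simulation.** Assumptions: 10 subjects, 4 treatments, one biopsy per subject and treatment, total SD 1, 30% of variance between subjects, one treatment shifted by 1 SD, overall F test at 5%.

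| Model | Power (about) |
|---|---|
| Treatment only (as stated) | 0.54 |
| Treatment + subject | 0.73 |
| Treatment + subject + TEER, ρ = 0 | 0.71 |
| Treatment + subject + TEER, ρ = 0.3 | 0.76 |
| Treatment + subject + TEER, ρ = 0.6 | 0.89 |

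Repeat runs differ by 0.01 to 0.02.

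*Check on the blocked model.* The squared deviations of the four treatment means (one at 1, three at 0) sum to 0.75² + 3 × 0.25² = 0.75. The noncentrality is 10 × 0.75/0.7 = 10.7 on 3 and 27 degrees of freedom, which gives power 0.73.

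*Check at ρ = 0.6.* The noncentrality is 10.7/0.64 = 16.7 on 3 and 26 degrees of freedom. This gives 0.90 before the small further loss from estimating the covariate slope, in line with the simulated 0.89.

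**4. False-positive rate.** In the same set-up the one-way residual estimates 0.3 + 0.7 = 1.0, whereas differences between treatments within subjects vary with 0.7 only. The F ratio is therefore too small on average under the null. Simulated type I error of the one-way ANOVA was about 0.4% to 1.5% against the nominal 5%, with subject shares of 50% and 30%.

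**The case against.** The strongest reply is that the covariate's benefit rests on a correlation the documents do not give. Nothing in them shows that starting resistance predicts FITC or HRP passage. Task 2 ties the two markers to paracellular and transcellular routes, so one resistance reading need not predict both. This stands. It is why the range above starts at ρ = 0, where adjustment gains nothing.

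A second reply is that most of the recoverable power may come from the subject block. In the illustration the block adds 0.19 (0.54 to 0.73), while the covariate adds about 0.03 at ρ = 0.3 and 0.16 at ρ = 0.6. This also stands, so the two changes belong in one model, with the block as the firmer part. The block does presuppose that subjects contribute biopsies to more than one treatment, which the documents imply but do not say.

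Third, TEER might be analysed as a change from its starting value, since its scale is not defined. That cannot be excluded. But a change score has variance 2(1 − ρ) relative to the raw value (taking equal variances before and after), so it helps only above ρ = 0.5, and it would leave FITC and HRP unadjusted.

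A reader might infer that a chance set of leaky biopsies could be mistaken for a treatment effect. The documents do not support that. With random allocation of biopsies, such imbalance is already inside the 5% error rate, and where subjects contribute to several treatments the unblocked test is conservative. Allocation is not described, so systematic imbalance is neither shown nor excluded.

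**Conclusion.** The point holds as a matter of precision. The stated model leaves subject and biopsy differences in the residual and in Tukey's HSD, and a better model is available at small cost. No bias and no excess of false positives is shown.

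The size is not fixed by the documents. Under the assumptions in the working, power moves from about 0.54 to 0.73 with the block, and to between 0.71 and 0.89 once the covariate is added, for ρ from 0 to 0.6. These are illustrations, not the power of this study. The covariate's gain is most plausible for TEER, where it is the same measurement on the same tissue, and less certain for FITC and HRP. Priority is low to moderate.

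**What to change.** - **Task 2:** state that TEER is recorded for every biopsy after mounting and immediately before the supernatant, stressor and markers are added. State also that each biopsy receives one condition, if that is the design.
- **Statistical Analysis:** replace the one-way ANOVA for FITC passage, HRP and TEER with a model of treatment + subject (block) + pre-exposure TEER (covariate). Take Tukey-adjusted treatment contrasts from that model. Define the time point and scale of the TEER endpoint.

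The cost is one extra reading per chamber on equipment already needed for an endpoint, and one degree of freedom for the covariate. If ρ is below about 0.2 the covariate brings little or no gain, and at ρ = 0 the illustration loses about 0.02 of power. Both terms should be fixed in the plan before any outcome data are examined.
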